4.0 Endpoints & Other Study Variables

Primary Outcomes of Intervention Feasibility and Acceptability: Follow CONSORT⁷³ guidelines and the example of Tickle-Dengnen (2013), we will track multiple indicators of trial feasibility:

Participant accrual: Accrual will be assessed using the mean weekly accrual rate throughout the duration of the study. Our feasibility criterion threshold is set at a mean weekly accrual of ≥ 2 participants per week.

Participant Randomization: We will assess feasibility of randomization in two ways. First we will assess the number of participants who refuse randomization versus the number randomized. Given our small sample of $n = 48$ participants, we will consider the randomization scheme feasible if ≤ 4 participants refuse randomization. We will consider our randomization scheme to be feasible by assessing the balance among the total number of participants allocated to each group at the end of the intervention. We will consider the randomization scheme feasible if group imbalance is $\leq 2\%$.

Participant retention: We will assess participant retention as the total number of participants that complete the week 13 data collection visit versus the number that were enrolled in the study expressed as a % retained. Based on a recent review of trial retention of physical activity and dietary interventions delivered to breast cancer survivors with MetS (Spark et al., 2013), which suggest that average trial retention rates across studies were 83%, we have set our feasibility criterion to be conservative at 80%.

Intervention engagement: Treatment sessions occur every 2 weeks. We will allow a 1-week window to make up missed sessions before we consider the session “missed”. We will assess

intervention engagement as the number of treatment sessions scheduled (n = 12) versus number attended (n = X), expressed as the % attended. Our feasibility criterion threshold for intervention engagement is a mean engagement rate of $\geq 80\%$.

Treatment satisfaction: We will assess treatment satisfaction at week 13 as the means score on the 8-item Client Satisfaction Scale.⁷⁵ Upon study completion, we will consider a mean score of ≥ 29 (range 8-32) on the client satisfaction scale to be satisfactory for consideration of a subsequent trial. In addition, after the week 13 final visit we will conduct qualitative semistructured interviews with a subsample of $n = 12$ participants to obtain their views about the survivorship transition and participation in health behavior programs, as well as impressions of the intervention and suggestions for improving it. Participants who agree to participate in the exit interview will be compensated an additional \$25 via a Visa pre-paid gift card.

Protocol adherence: Each session, coaches are required to document session adherence tracking sheets. We will track session adherence throughout the study to enable us to address training related issue with coaches, as well as at the end of the study. To evaluate protocol adherence (both at session level and study level), we will calculate the number of session components adhered to versus the number required as per the protocol tracking sheets.

Suitability of inclusion and exclusion Criterion: Throughout the intervention we will track the number of participants screened, the number who refused (and reasons why), and the number of screen fails due to failure to meet inclusion/exclusion criteria. We will conduct a post-study review with our consulting physician ([name]) to determine if further revision of the inclusion/exclusion criteria is warranted before progressing to a full trial.

Rationale for Secondary Measures: The trial includes two primary treatments: OT intervention to address unmet needs, and HD treatment to help foster healthy dietary and physical activity habits. OT intervention to address psychosocial and physical symptoms should lead to improvements in physical function and social participation and QOL, and reduction in unmet needs. Habit development training should lead to increases in behavioral automaticity (Habit strength). Habitually engagement in healthy dietary and physical activity behaviors should translate to improved clinical outcomes.

Data Collection Feasibility: We will evaluate the feasibility of data collection for the following primary and secondary behavioral and clinical measures at baseline and week 13. Feasibility of data collection will be assessed as the mean % missingness. The mean % missingness will be derived for each instrument individually and for the battery as a whole. Feasibility criterion thresholds for data collection feasibility are as follows. Data missingness for any individual instrument must be $\leq 97\%$ and missingness across the battery must be $\leq 95\%$.

Behavioral Measures: We will measure *Behavioral automaticity* using the following item ('Behavior X) is something I do without thinking') from the Self-Report Behavioral Automaticity Index (SRBAI).⁷⁶ The SRBAI is a validated self-report instrument that measures perceptions of behavioral automaticity for an identified behavior. A single item was chosen base on our own, and other's preliminary data that suggest that participants struggle to understand the full four SRHI items.⁷⁶⁻⁷⁷ The chosen item has shown satisfactory content and predictive validity, and convergent validity with its parent index.⁷⁶⁻⁷⁷ To track HD during the intervention, the

SRBAI will be administered to treatment condition participants every two weeks to assess changes in HD for their self-selected habits. Resources are not available as part of this exploratory/developmental project to objectively evaluate the co-secondary behavioral outcomes of dietary intake and physical activity engagement. We have, therefore, selected self-report measures intended to maximize data quality and that will be administered at weeks 0 and 13: Dietary Quality for two non-consecutive days (a trained RA will call participants and complete the ASA 24 with them) using the National Cancer Institute's ASA 24®⁷⁸⁻⁷⁹ and coded using the validated Alternative Healthy Eating Index,⁸⁰ The ASA can be accessed at the following URL, (<https://epi.grants.cancer.gov/asa24/>). We will measure Subjective Physical Activity Engagement using the *Yale Physical Activity Scale*.

Objective Physical activity (subsample of participants). We will collect data for baseline objective physical activity using the ActivPal⁷³ wireless activity tracker. The ActivPal is a wireless activity tracker that adheres to the thigh using Tegaderm. Participants will wear an ActivPal device on their thigh for seven days to collect data on total physical activity during their waking hours. The Activpal does not require any effort on the part of the participant once it is adhered. The RA will remove the tracker after a 7 day data collection period. In week 13 the researcher will call them again and ask them to wear the device again (for 7 days) during week 13.

We will collect data for Quality of life using the 26-item validated WHOQOL-BREF at weeks 0 and 13.⁸³ Physical Function will be measured using the 20-item NIH PROMIS Physical Function measure. Participation will be measured using the 8-item NIH PROMIS Ability to Participate in Social Roles and Satisfaction with Participation in Social Roles measures. With the exception of the NCI ASA, copies of all measures are included in the appendices.

Clinical Measures: We will collect data for MetS component factors by assessing changes from baseline to week 13 in Systolic blood pressure, Weight, Hemoglobin A1c (HbA1c), and Triglyceride and HDL levels. Anthropometry and biomarker measures will be collected in the clinic following established anthropometry guidelines.⁸⁴

Symptom burden: We will collect data for symptom burden in a subsample of participants using and Ecological Momentary Assessment (EMA) called Movisens XS. A subsample of participants will be asked to download the Movisens application on their phone via a QR code texted to the participant (Android phones only). The application will prompt participants twice per day (12 pm and 8pm) to answer questions about daily symptoms (e.g., fatigue or pain) on the phone. The severity of 13 common cancer-related symptoms (EMA appendix) during the previous two hours will be assessed on a 0–10 numerical rating scale, with 0 being “not present” and 10 being “as bad as you can imagine.” Participants will also be asked to rate the quality of their sleep (first thing in the morning only) and to describe, using free text, what they are doing at the time of the EMA prompt (e.g., washing dishes, watching TV). Participants will be asked to complete the symptom reporting throughout the intervention (12 weeks). It will take about 30-50 seconds to complete each report.

Demographic and Descriptive Variables of Interest (Measured at baseline): These include Health Literacy, measured using the Rapid Estimate of Adult Literacy⁸⁵; Depression,

using the Geriatric Depression Scale⁸⁶; *comorbidity*, using a comorbidity checklist; *cognitive function* using the 6-CIT, and Sociodemographic factors (e.g., age, gender, education).

Statistical analysis plan

As the aim of the study is to assess feasibility, descriptive statistics will be used to assess feasibility metrics. There are no plans to analyze outcomes for general inference.

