1.0 Objectives

The objective of the present study is to determine the feasibility of a manualized, theory based, occupational therapist delivered, preventative intervention to increase habit development (HD) of healthy dietary and physical activity behaviors, and reduce metabolic syndrome (MetS) among high-risk, rural breast cancer survivors (BCS). Using a pilot 1-arm pre-post design, we will implement an intervention that is personalized, low burden (the majority of interactions are telecoaching sessions), and delivered during the initial survivorship transition. To determine the feasibility and preliminary effects of the intervention 48 community-dwelling BCS (ages 18 and older) will receive the 12-week intervention consists of three home-based face-to-face consultations with the therapist, 9 weekly telecoaching sessions, and the use of implementation intentions, environmental modifications, and tailored text messages to support physical activity and dietary habit formation. Feasibility metrics will be collected throughout the intervention. To assess feasibility of data collection practices, data collection for proposed primary and secondary outcomes will be collected at baseline and post intervention (week 13). We hypothesize the intervention will be feasible to implement and satisfactory to participants. The one specific aim is:

Aim 1. To determine the feasibility and acceptability of the intervention for BCS. We will evaluate trial recruitment, trial engagement and retention rates, treatment satisfaction, and the feasibility of the data collection processes for the primary behavioral measures of HD and the primary clinical measures of MetS as well as the secondary measures of improved dietary quality, physical activity engagement, physical and social functioning, self-reported unmet needs, and quality of life.

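### Satisfaction scores and exit interviews come only from women reached at or after week 13, so the acceptability mean is at risk of upward bias from women lost earlier

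*Combined protocol and SAP*

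**What the plan says.** Acceptability is named in Aim 1 (section 1.0), and treatment satisfaction is listed among the primary feasibility and acceptability outcomes in section 4.0.

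- **Timing of the scale:** "We will assess treatment satisfaction at week 13 as the means score on the 8-item Client Satisfaction Scale".
- **Decision rule:** "we will consider a mean score of ≥ 29 (range 8-32) on the client satisfaction scale" to be satisfactory for considering a subsequent trial.
- **Interviews:** "after the week 13 final visit we will conduct qualitative semistructured interviews with a subsample of" 12 participants. No rule for selecting the 12 is given.
- **Retention:** counted as "the total number of participants that complete the week 13 data collection visit versus the number that were enrolled in the study", with the threshold stated as "we have set our feasibility criterion to be conservative at 80" per cent.
- **Sample:** section 1.0 states that "48 community-dwelling BCS (ages 18 and older) will receive the 12-week intervention".

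The trial procedures in section 3.0 schedule every participant for the week 13 clinic visit, whether or not she kept up with sessions. The statistical analysis paragraph at the end of section 4.0 limits the analysis to descriptive statistics. The document describes no earlier satisfaction measure, no questionnaire at withdrawal and no rule for missing satisfaction scores. Reasons are recorded for refusal at screening, but recording reasons for withdrawal after enrolment is not mentioned.

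**The concern.** The 29-point rule feeds a decision about a further trial, yet the mean is taken only over women who reach week 13. A woman lost before then contributes no score, and the natural reading is that she is not interviewed either. If such women tend to be less satisfied, the mean describes those who stayed and overstates how acceptable the intervention was to those who started it. The interviews, which are meant to collect suggestions for improvement, could also miss the people with most to say about why it did not suit them.

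The threshold lies only 3 points below the scale maximum of 32, so a passing completer mean has little room to absorb lower scores from the women who are missing.

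**Working it through.** The plan gives no derivation for the threshold of 29 or for the sample of 48, so there is no figure to reproduce. The check asks how many women can be unscored while retention passes, and how low their scores would have to be to change the decision.

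**Inputs.** From the document: 48 women (section 1.0); retention of 80%, threshold of 29 and scale range of 8 to 32 (section 4.0). Assumptions: 48 is both the number enrolled and the number treated, and the unscored women's mean is varied because the document gives no value.

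**Step 1: women who can be unscored.** 0.80 × 48 = 38.4, so 39 completers are needed. 39/48 = 81.25% passes; 38/48 = 79.2% fails. That leaves 48 − 39 = 9 women, and 9/48 = 18.75%.

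**Step 2: size of the overstatement.** Completer mean minus all-participant mean = (9/48) × (completer mean − unscored women's mean).

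| Gap in means (points) | Overstatement (points) |
|---|---|
| 0 | 0 |
| 1 | 0.19 |
| 5 | 0.94 |
| 9 | 1.69 |
| 21 (29 against 8) | 3.94 |

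**Step 3: tipping point.** The all-participant mean falls below 29 when the unscored women average less than (29 × 48 − 39 × completer mean)/9.

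| Completer mean | Calculation | Tipping mean |
|---|---|---|
| 29.5 | (1392 − 1150.5)/9 | 26.83 |
| 30 | (1392 − 1170)/9 | 24.67 |
| 31 | (1392 − 1209)/9 | 20.33 |

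**Step 4: retention at the cited average.** The plan reports from a review that "average trial retention rates across studies were 83" per cent. 0.83 × 48 = 39.84, so about 40 completers and 8 lost. With completers at 30, the tipping mean is (1392 − 1200)/8 = 24.0.

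**Step 5: whether the engagement criterion would catch it.** The criterion is a mean of at least 80% of 12 sessions. Taking all 48 women as the denominator (the plan states none), suppose 39 attend all 12 sessions and 9 attend one. Then (39 × 12 + 9 × 1)/(48 × 12) = 477/576 = 82.8%, which passes. Retention, engagement and satisfaction can therefore all pass with 9 women gone after one session.

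**Step 6: if fewer are treated.** Sections 3.0 and 4.0 also describe randomisation, which conflicts with the one-arm design and must be reconciled. Assuming 1:1 allocation, about 24 would be treated. Applying 80% to that arm, 0.80 × 24 = 19.2, so 20 must remain and up to 4 can be unscored. With completers at 30, the tipping mean is (29 × 24 − 20 × 30)/4 = 24.0. The conclusion does not change.

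**The case against.** A reader might infer that women who leave the intervention are excluded from the acceptability data. The document does not support that. Section 3.0 schedules all participants for week 13, and retention is defined by attending that visit, not by finishing sessions. A woman who stops sessions but comes to week 13 can be scored and interviewed. The women lost are those who miss week 13.

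A reader might also infer that the mean is biased upward. That is not shown: the document gives neither scores nor reasons for leaving, and if women leave for reasons unrelated to satisfaction the bias is zero.

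The other criteria give some protection. With 48 as the engagement denominator, if 9 women leave after 3 of 12 sessions, the other 39 must average (0.80 × 48 − 9 × 0.25)/39 = 92.7% attendance for engagement to pass. If the 9 attend none, the 39 need 38.4/39 = 98.5%. Heavy early loss would therefore often show up elsewhere. Satisfaction is also one of several indicators in a descriptive pilot, and the tipping values above mostly take retention at its lowest passing count.

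These points limit the claim but do not close the gap. Scheduling a visit does not ensure attendance, and the retention threshold itself allows for loss. Retention and engagement show that women left; neither adjusts the satisfaction mean or records what those women thought.

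**Conclusion.** The point holds as a risk. Satisfaction and interview data are planned only at or after week 13, with no provision for women lost earlier. Up to 9 of 48 women can be unscored while retention passes, or up to 4 if about 24 are treated. Whether that matters depends on how the unscored women would have answered. A 1-point gap moves the mean by 0.19, while with completers at 30 the decision reverses once the 9 average below 24.67.

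This rests on losses at the largest number the retention criterion allows, and on assumed scores for the missing women. It does not show that the criterion will be wrong. It shows that a pass at 29, as planned, would describe completers and could not by itself be read as acceptability to everyone who started.

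**What to change.** 1. Offer the eight items by phone or text at withdrawal, or at week 13 to women who miss the visit. Include everyone who had at least one session and agrees to contact.
2. Report the mean for that group against 29, alongside the completers-only mean.
3. Report the number scored out of the number treated, and the tipping-point mean for those still missing.
4. Record reasons for withdrawal after enrolment.
5. Open some of the 12 exit interviews to women who did not complete. How many is a matter of preference.

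The cost is about 9 short calls at the lowest passing retention (4 if about 24 are treated). The study already phones participants for the week 13 dietary recalls and uses coaching calls and texts, so no new contact route is needed. Some women will not respond, which the tipping-point value makes visible. The consent pages are not in the public document, so the terms for contact after withdrawal need checking.

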3.0 Study Design

Experimental Design and Methods

We will use a 1-arm pre-post design to examine the feasibility and preliminary effect of the intervention compared to enhanced usual care. We will randomize $n = 48$ BCS (ages 18 and older) with MetS, to either the treatment or enhanced usual care condition. All participants will complete baseline and follow-up data collection at weeks 0 and 13 respectively. To track habit formation during the intervention, treatment participants will complete a text message delivered, single item behavioral automaticity measure two weeks apart (week 0-2).

Trial Setting, Sampling, and Recruitment. We will recruit our sample of $n = 48$ BCS in collaboration with the Karmanos Cancer Institute’s Detroit hospital clinic. Trained RAs located at the clinics will screen, consent, and enroll eligible participants following an IRB approved protocol. We will also recruit participants from the Cancer Survivorship in Metropolitan Detroit study (IRB# 120714MP2F). We will submit a data request to obtain the contact information of participants who may meet the criteria for MetS and who have agreed to be contacted in the future about additional research studies (see recruitment below). A trained RA will then call the participant and using an IRB approved script, screen the potential participant for eligibility and provide an overview of the study.

Inclusion Criteria: English speaking, females ages 18 and older with a diagnosis of stage 1-3 histologically confirmed first cancer of the breast will be invited to participate. Three of the following 5 criteria must be present for MetS: a large waistline (> 40 inches for men and > 35 inches for women); systolic blood pressure ≥ 130 ; HbA1c of $\geq 5.7\%$; triglyceride levels > 150 mg/dL; and HDL cholesterol levels < 50 mg/dL. However, since we will be recruiting participants from a variety of setting, and not all sources will have available MetS data, we will use a modified classification criteria, based on recruitment source. Those procedures are described below.

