For eligible participants, the coordinator will next contact the participant and schedule the first of two baseline data collection visits. The first visit be in person and will consist of the participant completing psychosocial measures, a 24 hour dietary recall, and being shown how to use an activity tracking device to track their activity (if asked to complete this component) as well as be shown how to complete the symptom burden tracking (if selected to complete this component). The second visit will be conducted over the phone and consist of the RA completing the online dietary recall with the participant. Seven days after the first visit, and only if the participant was asked to either complete the activity tracking, an RA will visit the participant at their home to pick up the activity tracker.

The first intervention visit occurs 2 weeks after the participant completes baseline data collection (including any optional study activities). Participants will participate in the initial coaching session, followed by 11 additional sessions during weeks 2-12. We will schedule all participants for clinic-based follow-up data collection visits at week 13 where we will collect a consistent set of study measures. One exception to the clinic based data collection is the NCI dietary recall measure, which, similar to baseline data collection, will be conducted over the phone with the participant on two non-consecutive days during week 13. Participants will receive

a total of \$100 in compensation paid via pre-paid Visa cards for completing the weeks 0 and 13 study visits. Participants who complete the option data collection are eligible to receive an additional \$25 in compensation for their time and effort. Optional activities include symptom reporting, activity tracking and exit interview.

Treatment Description.

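### The data-collection feasibility limits run the wrong way: an instrument passes with up to 97% of its data missing and the battery with up to 95% missing

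*Combined protocol and SAP*

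**What the plan says.** The Data Collection Feasibility paragraph of section 4.0 covers the "primary and secondary behavioral and clinical measures at baseline and week 13". It names the metric: "Feasibility of data collection will be assessed as the mean % missingness". It gives the levels: "The mean % missingness will be derived for each instrument individually and for the battery as a whole". It then sets the limits: "Data missingness for any individual instrument must be $\leq 97\%$ and missingness across the battery must be $\leq 95" percent.

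On the schedule, section 3.0 states: "All participants will complete baseline and follow-up data collection at weeks 0 and 13 respectively". Aim 1 in section 1.0 lists feasibility of the data collection processes among the things the study is to determine. The statistical analysis paragraph at the end of section 4.0 plans descriptive statistics only, with no inference on outcomes. No other part of the document restates these limits, corrects them, or expresses them as completeness.

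**The concern.** A feasibility limit should fail a study whose data collection went badly. These limits cap missingness at 97% and 95%, so they pass almost any result. The neighbouring criteria in section 4.0 point the demanding way: 80% retention, mean engagement of at least 80%, and at most 4 refusals of randomization.

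The study has one aim and plans no inference, so its feasibility metrics are its result. A reader who applied the rule literally would report that data collection had met its criterion after losing most of the data. A reader who silently corrected it would have to choose the intended figures and denominator after the data were seen.

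**Working it through.** The limits are stated without any derivation, so there is no calculation of the plan's to reproduce. The check turns them into counts.

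**Inputs.** From the plan: 48 participants (sections 1.0, 3.0 and 4.0); two time points (sections 3.0 and 4.0); limits of 97% per instrument and 95% for the battery (section 4.0); an 80% retention criterion (section 4.0); 26 items in the WHOQOL-BREF (section 4.0). The plan does not say whether forms or items are counted, who is in the denominator, or whether time points are pooled, so each choice below is an assumption.

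**Formula.** Largest number missing that still passes = the whole-number part of (limit × N).

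**Denominators.** Two time points for all enrolled: 48 × 2 = 96. Retention passes at 39/48 = 81.25% and fails at 38/48 = 79.2%, so attendees only gives 48 + 39 = 87. WHOQOL-BREF items: 26 × 96 = 2,496.

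**Per-instrument limit, as written (≤97% missing):**

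| Counting assumption | N | Most missing that passes | First failure | Data needed to pass |
|---|---|---|---|---|
| Forms, one time point, all enrolled | 48 | 46 (95.8%) | 47 (97.9%) | 2 forms |
| Forms, pooled, all enrolled | 96 | 93 (96.9%) | 94 (97.9%) | 3 forms |
| Forms, pooled, attendees only | 87 | 84 (96.6%) | 85 (97.7%) | 3 forms |
| WHOQOL-BREF items, pooled | 2,496 | 2,421 (96.99%) | 2,422 (97.04%) | 75 items |

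In the last row, 75/96 = 0.78 answered items per form. The conclusion is the same in every row.

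**Battery limit (≤95% missing).** 5% of 96 is 4.8, so the battery passes with an average of about 5 of 96 forms per instrument. Not every instrument could sit at 3 of 96 at once, because the battery would then be 96.9% missing and fail. The number of instruments is not given, so no battery total is stated.

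**Chance of passing.** For one instrument at one time point (n = 48), assuming missing forms are independent, the rule passes with at most 46 missing. The exact binomial probability of passing is above 0.9999 when the true missing rate is 50%, 0.9997 at 80%, 0.96 at 90% and 0.70 at 95%.

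**Direct complement (missingness ≤3% and ≤5%).**

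- *Per instrument.* 2/96 = 2.1% passes and 3/96 = 3.1% fails. At one time point, 1/48 = 2.1% passes and 2/48 = 4.2% fails.
- *Battery.* If this is the share of participants with any instrument missing, 2/48 = 4.2% passes and 3/48 = 6.25% fails. If it is a mean over instruments, ≤3% on each already guarantees ≤5% overall, so the battery limit adds nothing.
- *Denominator.* With 39 of 48 retained, counting all enrolled gives 9/48 = 18.75% missing at week 13 and 9/96 = 9.4% over both time points. Both exceed 3% and 5% even if every attendee gives complete data.
- *Strictness.* With a true missing rate of 5% and independence, one instrument meets ≤3% with probability 0.30 at one time point (at most 1 of 48 missing). Pooled (at most 2 of 96), the terms for 0, 1 and 2 missing are 0.007 + 0.037 + 0.092 = about 0.14.

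**The case against.** The strongest reply is that this is a slip any reader will see through: the figures look like completeness targets of 97% and 95%. Missingness will be tabulated whatever the cut-off, no inference depends on it, and the plan attaches no stated consequence to failing this limit. Loss of participants by week 13 is already tested, because retention counts "the total number of participants that complete the week 13 data collection visit".

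Much of that stands, and it limits the harm. It does not supply a working rule. The document does not confirm the completeness reading. A single misread symbol is not the explanation either, since reversing only the inequality would require at least 97% missing. The flip also cannot be made silently: the denominator and the meaning of battery missingness change whether the corrected rule passes.

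Retention does not cover data missing among people who attend. Section 3.0 notes: "One exception to the clinic based data collection is the NCI dietary recall measure"; those recalls are done by phone. If retention counts only the clinic visit and time points are pooled, all 48 could be retained with every baseline recall done and none at week 13. Missingness would be 96/192 = 50%, and the instrument would pass.

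It is also fair to object that the complement is not the only possible intent. As written the battery limit is the tighter of the two; after the flip it is the looser. The replacement figures are therefore for the sponsor to confirm.

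**Conclusion.** The criterion is wrong as written and must be corrected. It detects only missingness above 97% per instrument or 95% across the battery, which is no realistic level of poor data collection. This rests on the plan's own wording and on 48 participants at two time points for an instrument given to everyone. It does not depend on the unstated counting unit, denominator or pooling. The pass probabilities additionally assume independent missingness. What is lost is the only pass/fail test for one named component of the single aim; descriptive reporting and the retention criterion are unaffected. That 97% and 95% were meant as completeness is likely but is an inference.

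**What to change.** Restate the rule in the intended direction. The direct complement would read: *Completeness must be at least 97% for each instrument and at least 95% across the battery (missingness at most 3% and 5%) [sponsor to confirm both figures].* With it, the sponsor should:

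- define battery missingness, for example as a mean over instruments or as the share of participants with any instrument missing;
- state the denominator. Participants attending the relevant time point is suggested, with drop-out counted under retention [sponsor to confirm];
- state whether forms or items are counted, and whether baseline and week 13 are pooled or judged separately;
- count the activity tracker and symptom EMA, if included, only among those asked to complete them;
- give the single automaticity item its own denominator. Section 4.0 has it every two weeks in treatment-condition participants, while section 3.0 describes a different schedule (weeks 0–2). Those two statements need reconciling first.

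The cost is a few sentences of protocol wording, with no new data or participants. The corrected rule is strict: it allows 2 of 96 forms missing per instrument, or 1 of 48 at a single time point. At a true 5% missing rate it would usually fail, so the sponsor should weigh that before confirming the figures.
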